9.1.5 EVENTS OF SPECIAL INTEREST

Each study intervention may have a unique list of ESIs. Refer to the relevant appendix.

9.1.6 REPORTING OF PREGNANCY

Pregnancies that occur in participants following study intervention initiation and while on-study will be recorded in the database, and participants will be discontinued from the study intervention (see Section 7.1 for discontinuation definition). Upon discovery of a pregnancy, the study team will ask pregnant participants to complete a pregnancy-specific consent form in order to follow the pregnancy to its outcome in case the outcome is not reached while the participant is on-study. Additionally, within 1 to 2 business days after learning of the pregnancy, the DCRI Safety Surveillance team will notify study-drug supplying partners of the pregnancy, as required. Lastly, any pregnancy-associated ESI or SAE should be reported if information can be collected and entered into the CRF.

10 STATISTICAL CONSIDERATIONS

10.1 STATISTICAL HYPOTHESES

Primary Endpoint:

1. Improvement in the EOI outcome measure(s) from the EOI compared to baseline in study intervention(s) vs control

Version 3.0 25JAN2024

Secondary:

- 1. Improvement in fatigue in the study intervention(s) vs control
- 2. Improvement in cognitive function in the study intervention(s) vs control
- 3. Reduction in PASC-related symptoms in the study intervention(s) vs control
- 4. Reduction in insomnia symptoms in the study intervention(s) vs control
- 5. Improvement in sleep duration, efficiency, and timing in the study intervention(s) vs control
- 6. Improvement in sleep-wake patterns in the study intervention(s) vs control

10.2 SAMPLE SIZE DETERMINATION

This study uses an adaptive platform trial design that will allow study interventions to be added or dropped from consideration based on accruing evidence of futility or efficacy. In such a design, the required sample size depends on both the number of study interventions tested and the ability to pool their control arms for analysis. Initial sample size estimates are based on a study with a single intervention and 1:1 allocation to active intervention or control. If additional study interventions are added later that can contribute to pooled control, the sample size will be adjusted accordingly.

Appendix-level sample size calculations are fully described within each appendix.

10.3 POPULATIONS FOR ANALYSES

Population for effectiveness analyses: mITT. The primary efficacy analysis will be based on a modified intention-to-treat (mITT) population, consisting of all randomized participants who were administered the study intervention or control at least once. All participants in the mITT population will be included and analyzed according to their randomly assigned treatment group.

Safety population. Safety analyses will be performed among participants in the mITT population who report administering study intervention or control at least once. Participants will be analyzed according to their actual treatment received.

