9.1.2 COLLECTION PERIOD OF AE AND SAE INFORMATION

Safety event collection will occur at the pre-specified study visits but all participants will be instructed to self-report concerns by calling the site.
Serious adverse events (SAEs), UADEs, or ESIs (per appendix) will be extracted by site personnel from the participant's medical record if the participant seeks medical care or if hospitalization occurs, each of which notifies the site to conduct follow-up.

Medical occurrences that begin before the first invasive study procedure (blood collection or nasal swab), but after obtaining informed consent, will not be considered an AE. The medical occurrence or condition will be captured on the Medical History electronic case report form (eCRF).

Non-serious AEs may be reported by the participant, but will not be collected into the study database as an AE or further assessed by the site or study personnel. Non-serious AEs that result in study intervention discontinuation will be identified as the reason for study intervention discontinuation in the study database and reported separately as an AE, and they will be collected from the start of study intervention administration through the end of the intervention.

Any AEs that are also classified as symptoms associated with PASC and collected during the study will not be collected as a safety event to the study database or further assessed by the site or study personnel because they will be collected as part of the PASC symptom dataset.

Serious adverse events (SAEs) will be collected from the first invasive study procedure (blood collection or nasal swab) through the End of Study for all appendices that use a study drug and through the EOI Clinic Visit for all appendices that include other interventions.

UADEs will be collected in the clinical database from the start of the intervention through the end of the intervention.

Adverse events (AEs) that qualify as an ESI, even if a non-serious AE, will be collected from the start of the study intervention through the End of Study (30 ± 3 days after EOI) for all appendices that use a study drug and through the EOI Clinic Visit for all appendices that include non-drug interventions.

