10.4.1 OVERALL STATISTICAL DESIGN

This study is a platform protocol designed to be flexible and consists of distinct symptoms of sleep disturbance using different interventional designs integrated into COVID-19 programs and subsequent treatment plans. For this study, data from all enrolled participants that receive the control intervention or treatment intervention will be included in the analyses. Between-group comparisons of the primary study endpoint, change from baseline in PROMIS SRI/SD T-scores (and sleep onset variability for Complex PASC-Related Sleep Disturbance), and clinically important secondary endpoints (eg, PROMIS 10a Fatigue, Neurocognitive Battery, etc.) will be analyzed using ANCOVA models. For endpoints that are categorized into binary secondary outcomes, logistic regression models will be utilized. Comparisons of the treatment groups for repeated measures outcomes over time will be investigated using mixed-

effect linear models with Generalized Estimating Equations (GEE) to account for correlated data withinparticipant.

Analyses of the primary endpoint measures, PROMIS SRI/SD T-scores (and sleep onset variability for Complex PASC-Related Sleep Disturbance), will require both the baseline and follow-up measurements. Participants missing one or both of their respective PROMIS SRI/SD measurements (or sleep onset variability) will not be included in the primary analysis cohort, ie, missing data on the primary endpoint will not be imputed in the primary analyses. However, sensitivity analyses will be conducted using imputation methods (eg, single or multiple imputation) to investigate the robustness of study findings. All testing hypotheses and estimated confidence intervals will be two-sided at a .05 significance level. The type I error rate of .05 for the secondary endpoints will be controlled using the Hochberg method.⁵⁰

Changes to the overall statistical design that occur prior to locking the study database will be detailed in the final SAP.

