10.4.3 ANALYSIS OF THE SECONDARY ENDPOINT(S)

The secondary endpoints listed below will be analyzed using ANCOVA linear regression models similar to the approach used in the primary endpoint:

- PROMIS 10a Fatigue total score
- Neurocognitive Battery total score
- ECog2 total score
- PASC Symptom Questionnaire total score
- ISI total score
- Sleep diary
 - Average nocturnal and 24-hour sleep duration and sleep efficiency
 - o Within-individual standard deviation of sleep onset
- Activity tracker
 - Within-individual standard deviation of sleep onset timing
 - o Average nocturnal and 24-hour sleep duration and efficiency

Comparisons of the treatment groups for endpoints with repeated measures outcomes over time will be investigated using mixed-effect linear models with GEE to account for correlated data within-participant.

If the null hypothesis is rejected for the primary outcome, then testing of the above secondary outcomes will be performed using the Hochberg method to control the type I error rate at 0.05. However, if the null hypothesis for the primary outcome is not rejected, then inferences on the secondary endpoints will be considered exploratory.

Safety endpoint. Safety endpoints include the proportion of participants who experience individual SAEs and the proportion who experience at least one or more SAEs. These will be analyzed in the safety population defined as the subset of mITT participants who confirm at least one administration of study intervention/control. Events of Special Interest (ESIs) will be summarized by the study intervention appendix and duration. The incidence of AEs/SAEs leading to discontinuation will also be summarized.

Other endpoints. Other secondary endpoints are either binary or continuous. Binary endpoints will be analyzed by logistic regression models to estimate the odds ratios [95% confidence intervals] between the treatment groups. Continuous endpoints will be analyzed using ANCOVA linear regression models.

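### The safety population counts only dosed participants who report or confirm a dose, so one who dies or is permanently lost before reporting drops out of the tabulated SAE proportions (minor)

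*Protocol*

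**What the plan says.** Section 10.3 defines the mITT population by what happened, "consisting of all randomized participants who were administered the study intervention or control at least once". The next paragraph defines the safety analyses by what the participant says: "Safety analyses will be performed among participants in the mITT population who report administering study intervention or control at least once". Section 10.4.3 states the restriction again, as a "safety population defined as the subset of mITT participants who confirm at least one administration of study intervention/control".

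The same paragraph of 10.4.3 places the SAE results in that set: "Safety endpoints include the proportion of participants who experience individual SAEs and the proportion who experience at least one or more SAEs". Section 10.4.1 is broader and says that "data from all enrolled participants that receive the control intervention or treatment intervention will be included in the analyses".

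SAEs can reach the database without any statement by the participant. Under section 9.1.2 they "will be extracted by site personnel from the participant's medical record if the participant seeks medical care or if hospitalization occurs". For appendices with a study drug the window opens before dosing: "Serious adverse events (SAEs) will be collected from the first invasive study procedure (blood collection or nasal swab) through the End of Study".

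**The concern.** Exposure is defined in two ways. Entry to mITT needs a dose; entry to the safety set needs a dose and a report of it. Calling the second set a subset of the first has content only if some dosed participants can fall outside it.

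Treatment is taken at home and use is checked later, mostly by phone. A participant who starts treatment and then dies or disappears before any such contact cannot report. If an SAE was found in the medical record, the trial would hold the event while its own definition keeps that participant out of the analyzed proportion.

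Membership would then depend on something that happens after randomization and that early serious harm can prevent. An arm that causes early harm would lose more of its cases. SAE counts may be low, so a single omitted case could be visible in the table.

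**Working it through.** No stated figure depends on this definition, so there is none to reproduce. The check has three parts.

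**1. Who falls outside the safety set (Protocol)**

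| Situation after a first dose | mITT (10.3) | Safety set (10.3, 10.4.3) |
|---|---|---|
| Reports or confirms at any later time | in | in |
| Hospitalized, confirms later | in | in |
| Dies before any report | in | out |
| Permanently lost before any report | in | out |

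The last row is final. Section 7.3 treats lost participants as withdrawn, and section 7.2 stops data collection at withdrawal while keeping what was collected before.

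**2. How many could be lost before a first dosing contact**

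Inputs:
- Attrition is 20% (13.7.1). Section 14.8.1 says that similar assumptions apply to Appendix B, so 20% is used there too.
- Total sample size is 474 in Appendix A and 600 in Appendix B.
- Dosing lasts 10 weeks (70 days) in Appendix A and 8 weeks (56 days) in Appendix B.
- First dosing contact is about day 5 in Appendix A (titration calls, Table 2 footnote) and about day 14 in Appendix B (two-weekly contacts, 14.6).
- Assumption, not in the documents: attrition falls evenly over the dosing period.

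Formula: share = 20% × (day of first contact ÷ days of dosing).
- Appendix A: 20% × 5/70 = 1.4%; 474 × 0.0143 = 6.8, about 7 participants.
- Appendix B: 20% × 14/56 = 5.0%; 600 × 0.05 = 30 participants.

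Under the even-loss assumption these are upper limits, because some of those lost never took a dose. The counts scale with the early loss rate: if losses came twice as fast at the start, both would double.

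**3. What this could do to the SAE proportion**

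The counts in part 2 are participants, not SAEs. The documents give no SAE rate. Assuming 1% to 4%, with no enrichment among early losses, the SAE cases involved are:
- Appendix A: 7 × 0.01 = 0.07 to 7 × 0.04 = 0.28.
- Appendix B: 30 × 0.01 = 0.3 to 30 × 0.04 = 1.2.

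Enrichment is the reason for concern. Leaving out a group lowers the proportion whenever the SAE rate in that group exceeds the rate in the whole arm. Illustration with 237 per group (13.7.1); the SAE counts and the number unconfirmed are assumptions:

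| All dosed | Left out | Confirmed only |
|---|---|---|
| 2/237 = 0.84% | 1 participant, 1 with SAE | 1/236 = 0.42% |
| 5/237 = 2.11% | 3 participants, 2 with SAE | 3/234 = 1.28% |
| 9/237 = 3.80% | 3 participants, 2 with SAE | 7/234 = 2.99% |

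**The case against.** The strongest reply is that the rule sets no deadline and names no particular contact, so one report at any time is enough. Participants who stop treatment stay in follow-up (7.1). They are asked to attend an Early Termination visit whose assessments match those at the End of Intervention visit, including the adherence evaluation (8.5, 8.6), and an End of Study call follows (8.7). SAEs are followed to resolution, and the event form records the action taken with study intervention (9.1.3). A reader might infer that hospitalized participants are excluded. The documents do not support that, except for those who never report afterwards. This part of the reply stands.

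A reader might also infer that the SAE vanishes from the trial or weakens the halting trigger of three related events. It does not. SAEs are still collected, entered within 24 hours and reported, and the DSMB reviews aggregate safety data (9.1.2, 9.1.4). Sections 13.3 and 14.3 count participants on study drug or active intervention and do not refer to the safety population. Only the tabulated proportion is affected.

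A larger count for Appendix B is tempting if the safety call at 30 ±7 days is taken as the first contact: 20% × 30/56 = 10.7%, or 64 of 600. Section 14.6 rules this out with contacts about every 2 weeks, and section 14.4.3 adds calls throughout the intervention.

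Finally, how a dose is confirmed may be called operational detail for the SAP, which was not available for this check. Nothing in the Protocol bars pill counts or sensor data as confirmation, and with home dosing mITT membership may rest on the same reports. This stands only in part. The Protocol itself fixes the membership rule twice, each time with the participant as the one who reports or confirms. If the two sets do coincide in practice, the same people leave both and the gap in the safety table remains.

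**Conclusion.** The point holds as a minor defect in a stated definition. Followed literally, sections 10.3 and 10.4.3 leave a dosed participant who dies or is permanently lost before ever reporting a dose out of the SAE proportions, even if the SAE is on record.

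The size is probably small: up to about 7 of 474 participants in Appendix A and 30 of 600 in Appendix B, given even attrition of 20% and first dosing contacts at about days 5 and 14. How many of these would have an SAE cannot be derived from the documents. The expected direction is downward, because an early serious event can be the very reason that no report was made. Sample size, power, type I error and the efficacy results are untouched.

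**What to change.** In sections 10.3 and 10.4.3, and in the SAP, use one definition: all randomized participants with at least one administration of study intervention or control by any available evidence, analyzed by actual treatment received. List what counts as evidence: participant or proxy report, pill count or returned product, lamp log or light-sensor data, or the medical record. Sections 6.2.1 and 14.4.2 and Tables 2 and 3 already provide for product return, pill counts, adherence checks, logs and the sensor.

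Do not presume exposure from dispensing alone in the main safety set. Both schedules distribute product at Day 0, ahead of a pre-intervention week, so that rule would admit people who never dosed, dilute the SAE proportion and could count SAEs that came before any dose. At most, use it as a sensitivity analysis.

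The cost is a wording change in two sections and the SAP, and slightly more work to classify exposure for the few participants without a report.

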10.4 STATISTICAL ANALYSES

This section describes the analytical methods for the primary, secondary, and safety outcomes. Full details will be provided in the SAP.

10.4.1 OVERALL STATISTICAL DESIGN

This study is a platform protocol designed to be flexible and consists of distinct symptoms of sleep disturbance using different interventional designs integrated into COVID-19 programs and subsequent treatment plans. For this study, data from all enrolled participants that receive the control intervention or treatment intervention will be included in the analyses. Between-group comparisons of the primary study endpoint, change from baseline in PROMIS SRI/SD T-scores (and sleep onset variability for Complex PASC-Related Sleep Disturbance), and clinically important secondary endpoints (eg, PROMIS 10a Fatigue, Neurocognitive Battery, etc.) will be analyzed using ANCOVA models. For endpoints that are categorized into binary secondary outcomes, logistic regression models will be utilized. Comparisons of the treatment groups for repeated measures outcomes over time will be investigated using mixed-

effect linear models with Generalized Estimating Equations (GEE) to account for correlated data withinparticipant.

Analyses of the primary endpoint measures, PROMIS SRI/SD T-scores (and sleep onset variability for Complex PASC-Related Sleep Disturbance), will require both the baseline and follow-up measurements. Participants missing one or both of their respective PROMIS SRI/SD measurements (or sleep onset variability) will not be included in the primary analysis cohort, ie, missing data on the primary endpoint will not be imputed in the primary analyses. However, sensitivity analyses will be conducted using imputation methods (eg, single or multiple imputation) to investigate the robustness of study findings. All testing hypotheses and estimated confidence intervals will be two-sided at a .05 significance level. The type I error rate of .05 for the secondary endpoints will be controlled using the Hochberg method.⁵⁰

Changes to the overall statistical design that occur prior to locking the study database will be detailed in the final SAP.

10.4.2 ANALYSIS OF THE PRIMARY ENDPOINT(S)

The primary efficacy analysis for the comparison of study intervention versus control will be based on the mean change in the primary endpoint among at-risk populations. Participants who complete the PROMIS SRI/SD T-scores at baseline and at EOI will be included in the primary analysis. Change from baseline comparison between groups for the PROMIS SRI/SD T-scores is defined as,

ABSOLUTE CHANGE = PROMIS SRI/SD [EOI] - PROMIS SRI/SD [Baseline],

where the EOI measurement is collected at the End of Intervention Clinic Visit. ANCOVA linear regression models will be implemented with change from baseline as the response variable and baseline PROMIS 8a T-scores as a covariate.

A similar analytic approach will be applied to sleep onset variability. The primary outcome(s) measure(s) will be defined per appendix. The outcome measure that is not chosen will be analyzed as a secondary outcome to the primary objective. Refer to the SAP for details.

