13.7 STATISTICAL CONSIDERATIONS (APPENDIX LEVEL)

13.7.1 SAMPLE SIZE DETERMINATION

An Analysis of Covariance (ANCOVA) linear regression model will be used to compare PROMIS-8a Tscores for the investigational intervention versus control at post-treatment measurement with an

adjustment for the baseline PROMIS-8a measurement. The key determinants of power include the number of participants (ie, sample size), the hypothesized difference in mean T-scores at follow-up for investigational intervention versus control among participants with similar baseline T-scores (ie, the treatment effect), and the standard error of the regression coefficient representing the mean difference in the ANCOVA model. A clinically meaningful treatment effect is assumed to be 5 T-score. The amount of statistical information about treatment effect (β_{trt}) can be quantified as $I = [Var(\hat{\beta}_{trt})]^{-1}$ which is the reciprocal of the estimated treatment effect variance in the primary analysis ANCOVA model. In order to detect a treatment effect of ($\beta_{trt} = 5$) with power $1 - \beta$ and two-sided type-I error α , the required amount of statistical information is given by I = { $(z_{\alpha/2} + z_{\beta})/5$ }² where $z_{\alpha/2}$ and z_{β} are the $(1 - \alpha/2)$ and $(1 - \beta)$ quantiles of the standard normal distribution. The sample size estimation is based on the rough approximation of $V(\hat{\beta}_{trt}) \approx \frac{4\sigma^2(1-R^2)}{n} \cong \frac{4\sigma^2}{n}$, when $R^2 \approx 0$, here σ^2 is the variance of PROMIS-8a T-scores within each treatment group, R^2 is the ANCOVA model's coefficient of determination, and n is the total sample size for active intervention plus control. If the estimated treatment effect is assumed to be 5 units, $\hat{\sigma} = 15$ units (ie, an effect size of .33), two-sided type I error of .05, thus the required total sample size for 90% power to detect a treatment effect of 5 T-score units is 379 participants. Accounting for a 20% attrition rate will lead to a total sample size of 474 participants, which is 237 participants per group (Figure 4).

Standard deviation

Figure 4. Sample Size Estimates Using the ANCOVA Model

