14.1.1 PRIMARY OUTCOME MEASURES AND ENDPOINTS

Primary: PROMIS 8b SD to assess sleep disturbance and activity tracker to assess sleep onset variability

Secondary outcome to the Primary Objective: PROMIS 8a SRI

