14.8 STATISTICAL CONSIDERATIONS (APPENDIX LEVEL)

14.8.1 RATIONALE FOR SELECTION OF DOSE

Complex PASC-related Sleep Disturbances is a 2X2 factorial design. There will be two independent primary endpoints, namely (1) PROMIS 8b SD and (2) variability in sleep onset. Thus, each endpoint will be tested at .025 type I error rate to maintain the overall error rate at .05. Similar assumptions as in Appendix A (Section 13.7.1) will be used to calculate the statistical power for PROMIS 8b SD endpoint, except using type I error rate at .025 level. A total of 560 participants is needed to detect a 5-unit difference between groups with at least 90% power. For the variability in sleep onset with type I error rate of .025, a total sample size of 600 participants is needed. The study will have at least 90% power to detect an effect size between .35 and .45, assuming variability in sleep onset of SD = 70 minutes in the control group and roughly SD = 45 minutes in the intervention group. Thus, this study will require a total of 600 participants to maintain at least 90% power for both primary endpoints.

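### Section 10.4.2 names baseline PROMIS 8a as the only ANCOVA covariate, which does not match Appendix B's PROMIS primary endpoint, 8b SD

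*Protocol*

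**What the plan says.** Protocol Section 10.4.2 defines the response as the EOI score minus the baseline score, written for SRI and SD together. The model sentence reads "ANCOVA linear regression models will be implemented with change from baseline as the response variable and baseline PROMIS 8a T-scores as a covariate". The section then adds "A similar analytic approach will be applied to sleep onset variability", without naming a covariate for that endpoint, and refers to the SAP for details. Section 10.4.3 says the secondary ANCOVAs follow an approach like the primary one, again without naming covariates.

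The 8a form is Sleep-Related Impairment and the 8b form is Sleep Disturbance. In Appendix A the primary endpoint is 8a SRI, and its sizing section (13.7.1) plans an "adjustment for the baseline PROMIS-8a measurement", so outcome and covariate match. In Appendix B, Section 14.1.1 states "Primary: PROMIS 8b SD to assess sleep disturbance and activity tracker to assess sleep onset variability"; there 8a SRI is only a secondary outcome to the primary objective.

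Section 14.8.1 names no covariate for Appendix B. It says "Similar assumptions as in Appendix A (Section 13.7.1) will be used to calculate the statistical power for PROMIS 8b SD endpoint", with the alpha changed: "each endpoint will be tested at .025 type I error rate to maintain the overall error rate at .05". Section 10.4.1 makes testing two-sided and requires both the baseline and the follow-up measurement of the primary endpoint for inclusion.

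**The concern.** The covariate sentence sits in the platform section and covers both scales, yet it is correct for only one of them. Followed literally, the confirmatory 8b analysis in Appendix B is a change score adjusted for baseline 8a. Baseline 8b enters by subtraction only, not as a covariate.

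The sizing takes a residual SD of 15. A change score that is not adjusted for its own baseline has residual variance 2·SD²·(1 − rho), which exceeds SD² whenever rho is below 0.5. Baseline 8a recovers only part of this. Chance imbalance between arms in baseline 8b would also be handled less well than by adjusting for 8b itself.

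The sentence also leaves room for argument after the data are seen. An analyst could defend the literal model (8a) or the evidently intended one (8b) for the same primary test.

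**Working it through.** **Inputs from the protocol.** Effect 5 T-score units, SD 15, 90% power, R² ≈ 0, 20% attrition (13.7.1, carried to Appendix B by 14.8.1); alpha .025 (14.8.1), two-sided (10.4.1); 560 for 8b and 600 in total (14.8.1). Each factorial margin is taken as 1:1.

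**Assumptions, not in the protocol.** Baseline-to-EOI correlation rho of 8b: 0.3 to 0.7. Baseline 8a–8b correlation r: 0 and 0.5, with 0.7 as a further case. Equal SD at both visits. 8a predicts later 8b only through baseline 8b. The 20% attrition applied to 600 gives 480 evaluable.

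**Step 1: reproduce the plan's figures.** N = 4·SD²·((z for alpha/2 + z for power)/5)².
- Appendix A: 900 × ((1.960 + 1.2816)/5)² = 378.3, so 379; 379/0.80 = 473.75, so 474. Both match.
- Appendix B, 8b: 900 × ((2.2414 + 1.2816)/5)² = 446.8, so 447; 447/0.80 = 558.75, so 559, against 560 stated.

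The 560 is sound on its own assumptions. With residual SD 15, power is 90.1% at 448 evaluable (560 less 20%) and 92.1% at 480.

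**Step 2: residual variance v, as a multiple of 15².**
- As written (change in 8b, baseline 8a as covariate): v = 2(1 − rho) − r²(1 − rho)².
- Own baseline (8b as covariate): v = 1 − rho².

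**Step 3: power** = Φ((5/15)·(√480/2)/√v − 2.2414) = Φ(3.6515/√v − 2.2414).

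Example at rho 0.3:
- r = 0: v = 1.40, 3.6515/1.1832 − 2.2414 = 0.845, power 80.1%.
- r = 0.5: v = 1.40 − 0.25 × 0.49 = 1.2775, power 83.9%.
- Own baseline: v = 0.91, power 94.4%.

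| rho | as written, r = 0 | as written, r = 0.5 | baseline 8b as covariate |
|---|---|---|---|
| 0.3 | 80.1% | 83.9% | 94.4% |
| 0.4 | 86.3% | 89.0% | 95.9% |
| 0.5 | 92.1% | 93.7% | 97.6% |
| 0.6 | 96.7% | 97.4% | 99.0% |
| 0.7 | 99.3% | 99.5% | 99.8% |

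With r = 0.7 the literal model gives 87.5% at rho 0.3 and 91.4% at rho 0.4. Power falls below 90% when rho is under about 0.46 (r = 0), 0.42 (r = 0.5) or 0.36 (r = 0.7).

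**Step 4: sensitivity to the equal-SD assumption.** Entry requires a T score of at least 60 on one of the scales (Section 5.1), which may compress the baseline spread. If the baseline SD is k × 15 and the EOI SD is 15, the unadjusted change score has v = 1 + k² − 2·rho·k. At rho 0.3, k = 0.8 gives v = 1.16 and 87.5% power; k = 0.7 gives v = 1.07 and 90.1%; k = 0.5 gives v = 0.95 and 93.4%. The comparable figure at k = 1 is 80.1%.

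**The case against.** The strongest reply is that this is Appendix A wording carried into the platform section, that the section refers to the SAP, and that any statistician would use baseline 8b for an 8b outcome. That is probably how the sentence arose. But the protocol does not leave the covariate open. It names one, and no other section corrects it for Appendix B.

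The reply is right on several matters of scope and size:

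- A reader might infer that both Appendix B primary endpoints are to be adjusted for 8a. The text does not say so. For sleep onset variability it promises only a similar approach, which can naturally be read as ANCOVA with that endpoint's own baseline, as in Appendix A. The same holds for Section 10.4.3. These are ambiguities.
- A reader might infer that 8b is analysed with no use of its baseline. It is subtracted in the response, and Section 10.4.1 requires it; only the covariate is missing.
- A reader might infer bias from regression to the mean. It acts on both randomised arms alike, so the wrong covariate costs precision and adds no systematic bias.
- A reader might infer that the power claim fails. The shortfall depends on a correlation the protocol does not state, disappears at rho 0.5 and above, and shrinks if the entry cut-off narrows the baseline SD. The sizing sets R² ≈ 0, so it took no credit for any covariate.

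**Conclusion.** The covariate named in Section 10.4.2 is wrong for Appendix B's 8b SD primary endpoint and should be corrected. For sleep onset variability and the secondary ANCOVAs the point is only that the covariate should be made explicit.

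The likely cost lies between nothing that matters (rho of 0.5 or more) and roughly 10 to 14 percentage points of power at rho 0.3 (94.4% less 83.9% or 80.1%). This holds for equal SDs of 15, 480 evaluable, two-sided alpha .025 and r between 0 and 0.5. Own-baseline adjustment is better at every correlation examined and never falls below 94%. The document does not support a claim that the sample size is wrong or that the trial will miss 90% power.

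**What to change.** In Section 10.4.2, replace the reference to baseline PROMIS 8a in the model sentence with: *the baseline value of the respective endpoint as a covariate (8a SRI when SRI is the outcome, 8b SD when SD is the outcome, and baseline sleep onset variability for that endpoint)*. The sleep onset variability sentence and the secondary ANCOVAs in Section 10.4.3 then inherit the same rule. The SAP should carry identical wording, settled before unblinding.

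The cost is one sentence. No new data, visits or participants are needed, because these baseline values are already collected and the primary ones are already required for inclusion in the analysis. The sample size does not change.
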